2.3 Safety objectives

Safety Objective:	Outcome Measures:
To evaluate the safety and tolerability of saxagliptin plus dapagliflozin vs dapagliflozin, and vs placebo at Week 16.	
 • AEs/Serious AEs (SAEs) • Vital signs • Clinical laboratory tests • Electrocardiogram (ECG; including date and time, and normal/abnormal) • Physical examinations

2.4 Exploratory objectives

Exploratory Objectives:	Outcome Measures:
To compare post-IP minus pre-IP EGP during the glucose turnover study at Week 15 in: - saxagliptin plus dapagliflozin vs placebo - dapagliflozin vs placebo.	
 • Post-IP minus pre-IP EGP (mg/kg) during glucose turnover study at Week 15.
For each secondary outcome measure, the comparisons between the following groups will be explored as exploratory objectives: - saxagliptin plus dapagliflozin vs placebo - dapagliflozin vs placebo	(as indicated in secondary measures)
To explore the mean change from Week -1 to Week 16 in plasma glucagon-like peptide-1 (GLP-1), glucose-dependent insulinotropic polypeptide (GIP), and free fatty acids (FFA) during OGTT in: - saxagliptin plus dapagliflozin vs dapagliflozin - saxagliptin plus dapagliflozin vs placebo - dapagliflozin vs placebo	
 • Change from Week -1 to Week 16 in plasma GLP-1 (pM/mL and AUC [pg/ml.time]), GIP (pg/mL and AUC [pg/mL.time]), and FFA (mmol/L and AUC [mmol/L.time]) during OGTT.
To explore the mean change from Week -2 to Week 16 in FFA in: - saxagliptin plus dapagliflozin vs dapagliflozin - saxagliptin plus dapagliflozin vs placebo - dapagliflozin vs placebo.	
 • Change from Week -2 to Week 16 in FFA (mmol/L and AUC).
To explore the mean change from Week 0 to Week 16 in waist to hip ratio, blood pressure (BP), and lipids within each treatment group and between: - saxagliptin plus dapagliflozin vs dapagliflozin - saxagliptin plus dapagliflozin vs placebo - dapagliflozin vs placebo	
 • Change from Week 0 to Week 16 in waist to hip ratio (cm), BP (mmHg), and lipids.

BECAUSE THE PRECISE TIME AT WHICH EGP INCREASES FOLLOWING DAPAGLIFLOZIN VARIES FROM ONE DIABETIC INDIVIDUAL TO ANOTHER (MEROVCI, 2014), WE ALSO WILL COMPARE THE MAXIMUM CHANGES IN EGP AND PLASMA INSULIN/GLUCAGON/C-PEPTIDE/EPINEPHRINE/NOREPINEPHRINE/ CORTISOL/GH/FFA DURING THE GLUCOSE TURNOVER STUDY, AS WELL AS CHANGES IN THESE VARIABLES AT SPECIFIC TIME POINTS IN SAXAGLIPTIN PLUS DAPAGLIFLOZIN VS DAPAGLIFLOZIN

3. SUBJECT SELECTION, ENROLLMENT, RANDOMIZATION, RESTRICTIONS, DISCONTINUATION, AND WITHDRAWAL

Each patient should meet all of the inclusion criteria and none of the exclusion criteria for this study. Under no circumstances can there be exceptions to this rule.

3.1 Inclusion criteria

For inclusion in the study, patients should fulfill the following criteria:

1. Provision of informed consent prior to any study-specific procedures.
2. Is able to read, understand, and sign the Informed Consent Forms (ICFs) and, if applicable, an Authorization to Use and Disclose Protected Health Information form (consistent with Health Insurance Portability and Accountability Act of 1996 legislation), communicate with the Investigator, and understand and comply with protocol requirements, including the use of diary and glucose meter measurements.
3. Age = 18-70 years.
4. Has a diagnosis of T2DM.
5. Has HbA1c $\geq 7.5\%$ and $\leq 11.0\%$ obtained at Screening.
6. Treated with a stable dose of metformin ≥ 1000 mg/day or stable dose of metformin (≥ 1000 mg/day) plus sulfonylurea (glipizide, ≥ 5 mg/day; glyburide, ≥ 5 mg/day; glimepiride, ≥ 4 mg/day) for at least 8 weeks prior to Screening.
7. Has a BMI of 20 to 45 kg/m² (inclusive) at Screening.
8. Is male, or is female, and meets all the following criteria:
 - Not pregnant or breastfeeding.
 - Negative pregnancy test result at Visit 1 (Screening).
 - Women of childbearing potential (WOCBP; [including perimenopausal women who have had a menstrual period within 1 year]) must practice and be willing to continue to practice appropriate birth control (defined as a method that results in a low failure rate, i.e., less than 1% per year, when used consistently and correctly, such as implants, injectables, hormonal contraceptives [pills, vaginal rings, or patches], some intrauterine contraceptive devices [levonorgestrel-releasing or copper-T], tubal ligation or occlusion, or a vasectomized partner) during the entire duration of the study. As applicable, all methods must be in effect prior to receiving the first dose of study medication.

3.2 Exclusion criteria

Patients should not enter the study if any of the following exclusion criteria are fulfilled:

Target Disease Exceptions

1. Clinically diagnosed with Type I diabetes .
2. History of diabetic ketoacidosis, hyperosmolar nonketotic coma, or corticosteroid-induced Type 2 diabetes.

Medical History and Concurrent Diseases

3. History of bariatric surgery or lap-band surgery, or either procedure is planned during the time period of the study.
4. History of any unstable endocrine, psychiatric, rapidly progressing, or unstable renal disease, or rheumatic disorder, as judged by the Investigator.
5. Patients who, in the judgment of the Investigator, may be at risk for dehydration or volume depletion that may affect the patient's safety and/or the interpretation of efficacy or safety data.
6. Has evidence of current abuse of drugs or alcohol or a history of abuse within the past 52 weeks that, in the Investigator's opinion, would cause the individual to be noncompliant.

Cardiovascular Conditions

7. Cardiovascular disease within 3 months of Screening (i.e., MI, cardiac surgery, revascularization, unstable angina, stroke, transient ischemic attack, or arrhythmia).
8. Presence or history of severe congestive heart failure (New York Heart Association Class III and IV [[CCNYHA 1994](#)]), unstable or acute congestive heart failure, and/or known left ventricular ejection fraction of $\leq 40\%$.

Note: Eligible patients with congestive heart failure, especially those who are on diuretic therapy, should have careful monitoring of their volume status throughout the study.

Kidney Conditions

9. Estimated (eGFR) $< 60 \pm 5$ mL/min/1.73 m² or a measured serum creatinine of > 1.4 mg/dL for female patients and > 1.5 mg/dL for male patients. If the serum creatinine is ≤ 1.4 (female) or ≤ 1.5 (male) and the eGFR is $\geq 60 \pm 5$ ml/min/1.73m², the subject is eligible to participate in the study.
10. Congenital renal glucosuria.

Hepatic Conditions

11. Significant hepatic disease, including, but not limited to, severe hepatic insufficiency and/or significant abnormal liver function defined as aspartate aminotransferase (AST) and/or alanine aminotransferase (ALT) of >3x upper limit of normal (ULN).
12. Serum total bilirubin (TB) >2 mg/dL.
13. History of, or currently have, acute or chronic pancreatitis or have triglyceride concentrations \geq 500 mg/dL at Visit 1 (Screening).
14. Suspicion that the patient is infected with an infectious substance according to World Health Organization risk categories A and B (see Appendix C).
15. Known severe hepatic disease, including chronic active hepatitis.
16. Positive serologic evidence of current infectious liver disease, including patients positive for hepatitis B viral antibody IgM, hepatitis B surface antigen, and hepatitis C virus antibody.

Hematological/Oncological Conditions

17. Malignancy within 5 years of Visit 1 (Screening), with the exception of treated in situ basal cell or squamous cell carcinoma of the skin.
18. Hematocrit of <34% for both males and females.

Prohibited Medications

19. Administration of any antihyperglycemic therapy, other than metformin or metformin/sulfonylurea, for more than 14 days (consecutive or not) during the 12 weeks prior to Visit 1 (Screening) and during the study unless per protocol for rescue.
20. Current treatment with potent cytochrome P450 3A4/5 inhibitors (e.g., atazanavir, clarithromycin, indinavir, itraconazole, nefazodone, nelfinavir, ritonavir, saquinavir, and telithromycin).
21. Administration of any other investigational drug or participation in any interventional clinical studies 30 days prior to Visit 1 (Screening).
22. Treatment with systemic corticosteroids for the last 3 months prior to Visit 1 (Screening).
23. Prescription or over-the-counter weight loss medications within 3 months prior to Visit 1 (Screening).

Other

24. Patients with abnormal thyroid stimulating hormone (TSH) or free thyroxine (T4) values at Visit 1 (Screening) will be excluded.
25. Has a clinically significant medical condition that could potentially affect study participation and/or personal well-being, as judged by the Investigator.
26. Has clinically significant abnormal laboratory test values (clinical chemistry, hematology, and urinalysis) as judged by the Investigator at Visit 1 (Screening).
27. Has known contraindications, allergies, or hypersensitivities to any study medication or excipient as outlined in the IBs or local package inserts for saxagliptin and dapagliflozin.
28. Has a contraindication to metformin use, including known metabolic or lactic acidosis, or any condition associated with hypoperfusion, hypoxemia, dehydration, or sepsis.
29. Is currently pregnant (confirmed with positive pregnancy test) or breast feeding.
30. Is on a commercial weight loss program with ongoing weight loss more than 5% over the last 3 months prior to Visit 1 (Screening), or is on an intensive exercise program.
31. Involvement in the planning and/or conduct of the study (applies to both the study sponsor staff and/or staff at the study site).
32. Patient with any condition that, in the judgment of the Investigator, may render the patient unable to complete the study or which may pose a significant risk to the patient or patient suspected or with confirmed poor protocol or medication compliance.
33. Previous randomization in the present study.

3.3 Subject enrollment and randomization

Investigator(s) should keep a record, the patient screening log, of patients who entered pre-study screening.

The Investigators will:

1. Obtain signed informed consent from the potential patient before any study-specific procedures are performed.
2. Assign potential patient a unique enrollment number.

3. Determine patient eligibility in accordance with inclusion/exclusion criteria.
4. Assign an eligible patient unique randomization code.

If a patient withdraws from participation in the study then his/her enrollment/randomization code cannot be reused.

3.3.1 Procedures for randomization

Patients who meet all study requirements based on inclusion and exclusion criteria will be randomized to 1 of 3 treatment groups (while continuing on metformin therapy) at Visit 3 (Randomization):

- saxagliptin 5 mg + dapagliflozin 10 mg;
- dapagliflozin 10 mg + placebo for saxagliptin;
- placebo for dapagliflozin + placebo for saxagliptin.

Stratification will be conducted according to baseline HbA1c level ($\leq 8.5\%$ or $>8.5\%$) and baseline therapy (metformin or metformin/sulfonylurea). Randomization codes will be assigned strictly sequentially within each stratum as patients become eligible for randomization. The HbA1c level collected at Visit 1 (Screening) will be used as the baseline HbA1c level for randomization purposes.

If a patient is discontinued from the study, his/her randomization or enrollment number will not be reused, and the patient will not be allowed to re-enter the study. Randomized patients who discontinue early from the study will be replaced to ensure adequate patient number as described in the sample size calculation.

If a randomization number is allocated incorrectly, no attempt should be made to remedy the error once study material has been dispensed. The patient will continue with the allocated number and study material. Subsequent patients will continue using the first unallocated randomization number in the original numbering sequence.

3.4 Procedures for handling incorrectly enrolled or randomized subjects

Patients who fail to meet the eligibility criteria should not, under any circumstances, be enrolled or receive study medication. There can be no exceptions to this rule. Patients who are enrolled, but subsequently found not to meet all the eligibility criteria must not be randomized or initiated on treatment, and must be withdrawn from the study.

Where a patient does not meet all the eligibility criteria but is randomized in error, or incorrectly started on treatment, the Investigator will decide whether to continue or discontinue the patient from treatment.

Methods for assigning treatment groups

After written informed consent has been obtained, the patient will be assigned an enrollment code that is patient specific. The code will be used to identify the patient throughout study participation. Patient eligibility will be established before treatment randomization. Patients will be randomized strictly sequentially within each baseline (Visit 1) HbA1c stratum and baseline treatment (metformin and metformin/sulfonylurea) status at Visit 3 (Week 0), as patients are eligible for randomization. Assignment to treatment groups will be determined by a computer-generated random sequence.

The number and size of tablets will be identical for the investigational products (IPs) for the 3 treatment arms. Clinical supplies will be identified by randomization kit numbers, where each kit number is specific to a treatment arm. If a patient discontinues from the study, the patient code and randomization number will not be reused, and the patient will not be allowed to re-enter the study.

The site will randomize patients by allocating the lowest available randomization code in sequential order within the stratum (baseline HbA1c $\leq 8.5\%$ or $>8.5\%$) and baseline treatment (metformin or metformin/sulfonylurea) status. Randomization will be balanced in blocks within each baseline HbA1c stratum and baseline treatment status and each center.

Methods for ensuring blinding

Blinding is ensured by using a double-blind, single-dummy technique. Patients, the Investigator, and study site personnel involved with data review and analysis will be blinded throughout the study until database lock. The active tablets and the respective placebo tablets will be identical in size, color, smell, and taste. The bottles with IPs will be labelled with unique identification numbers.

No member at the study site handling data will have access to the randomization scheme during the conduct of the study, with the exception of the individual generating the randomization scheme.

In order to allow emergency unblinding, code envelopes with randomization codes only will be provided to the sites along with the drug supplies.

3.7 Methods for unblinding

Individual treatment codes, indicating the treatment randomization for each randomized patient, will be available to the Investigator(s) or pharmacists at the study site.

The treatment codes, as sealed paper code envelopes, should not be broken except in medical emergencies when the appropriate management of the patient requires knowledge of the treatment randomization.

The Principal Investigator retains the right to break the code for SAEs that are unexpected and are suspected to be causally related to an IP and that potentially require expedited reporting to

regulatory authorities. Treatment codes will not be broken for the planned analyses of data until all decisions on the evaluability of the data from each individual patient have been made and documented.

3.8 Restrictions

Once screened and qualified for entry, patients will be instructed as follows:

- Fast overnight for at least 10 hours prior to each study site visit, i.e., no food or beverage except water. Allowed medications can be taken with water only.
- Continue metformin or metformin/sulfonylurea therapy at current dosage and at approximately the same time each day, except that any morning dose of metformin or metformin/sulfonylurea should be delayed on the morning of study site visits.
- Delay administering the IPs (as applicable) and metformin or metformin/sulfonylurea on the morning of the clinic visit and bring study medication and metformin or metformin/sulfonylurea to each site visit.
- Refrain from alcohol intake and intense exercise 24 hours prior to each visit and recommend to not use tobacco/nicotine within 12 hours prior to each visit.
- Do not donate blood for the duration of the study and for 3 months following the last study visit.
- Comply with prescribed dosing regimen to preserve study integrity and ensure patient safety.
- Discuss any new prescriptions and over-the-counter or herbal/nutritional therapies with the Investigator, as concomitant use could result in alterations to their glycemic control and may place them at risk for significant hypoglycemic episodes.
- Make every attempt to adhere to the diet and exercise counselling and to the protocol visit schedule.
- Women must immediately contact the Investigator if they suspect they might be pregnant and if they have changed or plan to change their birth control method.

If a patient comes to a visit without having followed the above instructions then the patient should be re-scheduled for the entire visit (if possible within the allowed time-window).

3.9 Discontinuation of investigational product

Patients may be discontinued from IPs in the following situations:

- Patient decision. The patient is at any time free to discontinue treatment, without prejudice to further treatment.
- Patient experiences an AE or SAE that, in the Investigator's opinion, necessitates discontinuation from study medication.

- The Investigator decides that the patient should discontinue study medication. If this decision is made because of an SAE or a clinically significant abnormal laboratory value, appropriate measures will be taken.
- Severe noncompliance with the study protocol.
- Creatinine clearance $<60 (\pm 5) \text{ mL}/\text{min}/1.73 \text{ m}^2$ for sustained period of time, according to the Investigator's judgment.
- Initial and repeat laboratory tests meet any of the following criteria (see Appendix C):
 - ALT and/or AST are $>3 \times \text{ULN}$ and TB $>2 \times \text{ULN}$
 - ALT and/or AST are $>5 \times \text{ULN}$ for ≥ 14 consecutive days, at any time after initial confirmatory results
 - ALT and/or AST are $>8 \times \text{ULN}$
- Hypoglycemic episodes.

3.9.1 Discontinuation guidelines for protocol-defined major hypoglycemia episodes or recurrent non-major hypoglycemia episodes

Patients should not be discontinued from any treatment phase based on single episodes of hypoglycemia or symptoms of hypoglycemia unless clinically indicated. The assessment of a single finger stick or laboratory glucose value should not be the sole assessment used to determine patient discontinuation for hypoglycemia.

Clinical indications for discontinuation because of hypoglycemia may include the following:

- Multiple occasions of episodes outlined below that, in the opinion of the Investigator, indicate that continued treatment with study therapy is not in the best interest of the patient. This includes, but is not limited to:
 - Symptoms suggestive of hypoglycemia (e.g., sweating, shakiness, increased heart rate, confusion, dizziness, light-headedness, or hunger) in the absence of environmental factors known to contribute to hypoglycemia (i.e., excess physical activity, concurrent illness, or missed or delayed meal) **and/or**
 - Documented finger stick glucose values $<54 \text{ mg}/\text{dL}$ ($<3.0 \text{ mmol}/\text{L}$).
- A patient may also be discontinued from the study because of severe hypoglycemia, as determined by the Investigator.

If finger stick glucose values are discordant from glycemic control assessed by the laboratory or with clinical symptoms, the patient's glucose meter should be tested and the instructions for use reviewed with the patient.

- A patient may be discontinued from the study because of the development of ketoacidosis.

3.9.2 Procedures for discontinuation of a subject from investigational product

At any time, patients are free to discontinue IP or withdraw from the study (i.e., IP and assessments – see Section 3.10), without prejudice to further treatment. A patient who decides to discontinue IP will always be asked about the reason(s) and the presence of any AEs. If

possible, the patient will be seen and assessed by an Investigator(s). Any AEs will be followed up; patient diaries and all study drugs should be returned by the patient.

Patients who discontinue from the study medication will have an Early Termination Visit equivalent to the Week 16 assessments plus a glucose turnover study at the time of study medication discontinuation. The following data will be collected and entered onto the clinical database:

- Concomitant medication
- AEs

In the case of a decision to discontinue treatment, the Investigator will follow the patient until the event has resolved or stabilized, at least until Week 16.

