4. STUDY PLAN AND TIMING OF PROCEDURES

[Table 1](#) presents the schedule of assessments for this study.

Table 1 Study Plan

Evaluation	Screening	Run-in	Treatment Period					End of treatment/Early Termination or Rescue ^a
			1	2	3	4	5	
Visit	1	2	3	4	5	6	7	8
Week	-2	-1	0	4	8	12	15	16
Relative to Randomization (days)	-14	-9	R	28	56	84	103	112
Visit Window (±days)	(+7)	(±4^b)	0	(±5)	(±5)	(±5)	(±5)	(±4^b)
Obtain Informed Consent	X							
Review Medical and Surgical History	X							
Review Eligibility Criteria (Inclusion/Exclusion Criteria)	X							
Review Randomization Criteria			X					
Verify Patient Fasted 10 Hours	X	X	X	X	X	X	X	X
Complete Physical Examination	X							X
Brief Physical Assessment (at the Investigator's discretion)				X	X	X	X	
Body Weight	X		X	X	X	X	X	X
Height	X							
Body Mass Index	X							X
Vital signs (reclining/standing BP and HR)	X		X	X	X	X	X	X
Waist and Hip Circumference	X		X	X	X	X		X
12-lead ECG	X							X
Review Concomitant Medications ^c	X	X	X	X	X	X	X	X
Provide Diet and Exercise Counseling	X		X		X			
Verify IP Compliance				X	X	X	X	X
Dispense Study Medication			X	X	X	X		
Provide Glucose Meter and Supplies/Instructions for 7-point SMBG		X						
Perform 7-point SMBG Prior to Site Visit			X ^d	X	X	X	X ^d	X

Evaluation	Screening	Run-in	Treatment Period					End of treatment/Early Termination or Rescue ^a
	1	2	3	4	5	6	7	8
Visit	-2	-1	0	4	8	12	15	16
Week	-14	-9	R	28	56	84	103	112
Relative to Randomization (days)	(+7)	(±4 ^b)	0	(±5)	(±5)	(±5)	(±5)	(±4 ^b)
Review 7-point SMBG and hypoglycemia episodes			X	X	X	X	X	X
Collect Glucose Meter/Unused Supplies								X
Collect unused study medication								X
Dispense Rescue Medication (if needed)					X	X	X	
Assess AEs		X	X	X	X	X	X	X
Pregnancy Test (urine and serum if urine test positive) WOCBP only	X	X	X	X	X	X	X	X
Clinical Chemistry, Hematology ^c	X				X			X
eGFR and Serum Creatinine	X	x	x	x	X	x	x	X
HbA1C	X	X		X	X	X	X	X
FPG/ketones	X	X	X	X	X	X	X	X
Fasting Serum Lipids ^f	X	X			X		X	X
Thyroid function (TSH and T4)	X							
FFA	X							X
Urinalysis ^e	X							X
Double Tracer OGTT ^h with IC		X						X
Glucose Turnover Study ⁱ			X				(X) ^j	
DEXA	X							X

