Abbreviations: AE adverse event, β -hCG beta subunit of human chorionic gonadotropin, BP blood pressure, CrCl creatinine clearance, DEXA Dual Energy X-ray Absorption, ECG electrocardiogram, FFA free fatty acids, FPG fasting plasma glucose, GIP glucose-dependent insulinotropic polypeptide, GLP-1 glucagon-like peptide-1, HbA1c hemoglobin A1c, HDL high-density lipoprotein, HR heart rate, IgM immunoglobulin M, IP investigational product, LDL low-density lipoprotein, OGTT oral glucose tolerance test, R randomization, SMBG self-monitored blood glucose profile, T4 thyroxine, TSH thyroid stimulating hormone, WOCBP women of childbearing potential, IC = indirect calorimetry.

- ^a Early Termination procedures are to be completed for all patients who terminate the study or are rescued before Visit 8 (Week 16) of the Treatment Period. Discontinued patients should return to the study site and complete a glucose turnover study and all assessments required for Visit 8 (Week 16) 3 to 5 days later.
- ^b The glucose turnover study at Visit 3 should take place 5 to 14 days after OGTT at Visit 2. The Visit 7 glucose turnover study should take place approximately 10 days prior to OGTT at Visit 8.
- ^c Review of concomitant medications includes over the counter drugs and herbal/nutritional therapies.
- ^d 7-point SMBG should not be performed the day immediately before clinic visit 3 and 7.
- ^e Details for safety laboratory variables are shown in [Table 5](#).
- ^f Serum lipids include total-cholesterol, LDL-cholesterol, HDL-cholesterol, non-HDL cholesterol, and triglycerides.
- ^g Hepatitis panel includes hepatitis B viral antibody IgM, hepatitis B surface antigen, and hepatitis C virus antibody.
- ^h The double tracer OGTT will include blood draws for plasma glucose, plasma insulin, plasma C-peptide, plasma glucagon, plasma GLP-1, plasma GIP, plasma ³H-glucose, ¹⁴C-glucose specific activities (until Time 300 minutes) and urine will be collected.
- ⁱ The glucose turnover test will include blood draws for glucose, insulin, C-peptide, glucagon, cortisol, growth hormone, adrenaline, and noradrenaline; and ³H-glucose specific activities (until Time 300 minutes); and urine will be collected. Glucose turnover tests will include administration of IP at Time 0.

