- ^j Patients who are receiving rescue therapy or are early terminating: glucose turnover study will be performed 5 to 14 days prior to OGTT and Visit 8 assessments will also be completed prior to rescue. Glucose turnover study and Visit 8 procedures will be performed again at end of treatment for rescued patients.

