5.1.8 Glucose turnover study

A glucose turnover study will be performed according to schedule presented in Table 1. A glucose turnover study will be performed at Visit 3, which should be 5 to 14 days after the OGTT (Visit 2). An end of treatment glucose turnover study will be performed at Visit 7 and should be done approximately 10 days prior to the OGTT.

Patients will report to the study site after a 10-hour overnight fast and should be asked to void before beginning the glucose turnover study. At approximately 0600 (Time -180 minutes), a catheter will be placed into an antecubital vein and a primed (25 micro Curie [μCi] x FPG/100 up to a maximum of 50 μCi) – continuous infusion of [$3\text{-}^3\text{H}$]-glucose will be started]. The continuous infusion (0.25 $\mu\text{Ci}/\text{min}$) of [$3\text{-}^3\text{H}$]-glucose will be started and will be maintained throughout the study duration. A second catheter will be placed retrogradely into a vein on the dorsum of the hand, which will be placed in a heated box (50-60°C) for arterialized blood withdrawal. Prior to oral administration of study medication (saxagliptin, dapagliflozin, placebo), blood samples will be taken at the timepoints indicated in Table 3 for measurement of plasma glucose, insulin, C-peptide, glucagon, counter-regulatory hormones (i.e., plasma cortisol, growth hormone, adrenaline, and noradrenaline), and [$3\text{-}^3\text{H}$]-glucose specific activity. During the glucose turnover study, patients will receive assigned study medication 3 hours after the start of [$3\text{-}^3\text{H}$]-glucose infusion (Time 0). Blood samples will be obtained according to the timepoints indicated in Table 3 until the end of the study (Time 300 minutes/5 hours after drug is received). Metformin or metformin/sulfonylurea will **NOT** be taken until after the glucose turnover study has been completed.

Urine will be collected from the start of the study (Time -180 minutes) until Time 0 and again from Time 0 to 300 to measure urinary volume and urinary glucose concentration (to quantitate urinary glucose excretion). The glucose turnover study will end 5 hours after receiving study medication (Time 300 minutes) and patients will be given a meal and metformin or metformin/sulfonylurea and allowed to return home.

Table 3 Glucose Turnover Study

Timepoint (clock time)^a	Glucose	3-³H-glucose	Insulin/ C-peptide	Glucagon	CR hormones^b
-180 (0600)	X	X			
-30	X	X	X	X	X
-20	X	X			
-10	X	X	X	X	X
-5	X	X			

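### The early-termination glucose turnover study includes a full dose of study drug, and no supplied text withholds it when the drug was stopped for an adverse event, renal or hypoglycemia reason

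*Combined protocol and SAP*

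**What the plan says.** Section 3.9 lists the grounds for stopping IP. They include patient decision, an AE or SAE, investigator decision, severe noncompliance, sustained low creatinine clearance, liver test thresholds and hypoglycemia. For all of them, section 3.9.2 says the patient "will have an Early Termination Visit equivalent to the Week 16 assessments plus a glucose turnover study at the time of study medication discontinuation".

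Table 1 footnote a adds: "Early Termination procedures are to be completed for all patients who terminate the study or are rescued before Visit 8", and then: "Discontinued patients should return to the study site and complete a glucose turnover study and all assessments required for Visit 8".

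The Table 1 row headed "Glucose Turnover Study" carries footnotes i and j. Footnote i states: "Glucose turnover tests will include administration of IP at Time 0". Footnote j brings early terminators onto the same row: "Patients who are receiving rescue therapy or are early terminating: glucose turnover study will be performed 5 to 14 days prior to OGTT".

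Section 5.1.8 ties the procedure to that table ("A glucose turnover study will be performed according to schedule presented in Table 1") and repeats the dosing step: "During the glucose turnover study, patients will receive assigned study medication 3 hours after the start of" the tracer infusion.

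**The concern.** Each rule is reasonable alone. The primary endpoint is the acute EGP response to a dose, so a turnover study without a dose cannot yield it, and collecting endpoint data before a patient leaves treatment is good practice. The difficulty comes when the rules are combined for a patient in whom the drug has just been judged harmful. Site staff following the text would give that patient another full dose. Withholding it would depart from footnote i and section 5.1.8.

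What is at stake is patient safety, not the trial's inference. The hypoglycemia case shows it most clearly: section 3.9.1 bases that stop on the investigator's opinion that carrying on with study drug does not serve the patient, and the test then doses the patient in a prolonged fast.

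**Working it through.** The plan gives no figure to reproduce. The check is a cross-reading with a little arithmetic.

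**1. Who has the test.** Section 3.9.2 is mandatory in tone and is triggered by stopping study medication. It has no filter by reason.

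**2. What the test contains.** Footnote i and section 5.1.8 both place IP at Time 0 without qualification. Footnote j sits on the same row and names early terminators, so the row's test is also the early-termination test.

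**3. How large the dose is.** Section 6.8 allows no dose reduction. In the active arms the dose is dapagliflozin 10 mg, with or without saxagliptin 5 mg.

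**4. Whether anything withholds the dose.**

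| Reason for stopping | Text that would withhold the Time 0 dose |
|---|---|
| AE/SAE | None found |
| Sustained low creatinine clearance | None found |
| Hypoglycemia | None found |
| Liver criteria | Cannot be determined: section 3.9 points to Appendix C, not supplied |
| Pregnancy | Withheld: 5.2.1.4 requires a negative test before any in-clinic dose, and 6.7.1 stops all study medication at once |
| Ketoacidosis | None found if handled as an AE stop of IP; 3.9.1 words it as leaving the study, where 3.10 only encourages the procedures |

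**5. Timing.** Two readings of section 3.9.2 are possible.

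- The test is a last on-drug visit. The dose then comes after the decision to stop but before the stop takes effect.
- The test follows the stop. Footnote a, which has patients already described as discontinued come back, points this way.

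On both readings, a dose is given after the decision to stop.

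**6. Circumstances of the dose (section 5.1.8).**

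- Fast at dosing: 10 h overnight + 3 h tracer period = at least 13 h.
- Fast until the meal: 13 h + 5 h after the dose = at least 18 h.
- Safeguards: dosing is supervised, glucose is drawn every 15 minutes from 15 to 300 minutes, and metformin/sulfonylurea is not taken until the test ends.

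**7. What the dose buys (Table 3).**

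- Pre-IP glucose/tracer samples at -180, -30, -20, -10, -5 and 0 minutes: 6.
- Post-IP samples every 15 minutes to 300 minutes: 300 / 15 = 20.
- Total: 6 + 20 = 26, matching the table's own count.

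Section 8.5.1 excludes early terminators from the primary analysis. Their post-IP values could at most feed the sensitivity analyses on all available data, which section 8.5.4 makes optional.

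**The case against.** The strongest reply is that no single sentence orders IP for a patient stopped for harm. Section 3.9.2 is the specific text for stopped patients; it does not mention dosing and has study drug returned. Section 5.1.8 names only the Visit 3 and Visit 7 tests. Section 3.9 expects suitable measures after an SAE or laboratory stop, and section 7.2 leaves visit-day dosing to the direction of site staff. An investigator could be expected to withhold the dose.

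Part of this stands. The requirement comes from reading several places together, and footnote a is not clear about which patients it means: it opens with those leaving the study or being rescued. Certainty about a dose given days after the stop is therefore not available. But none of the softening texts says that the test runs without IP, while footnote i says that it includes IP. A safe course should not depend on departing from a stated procedure.

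A reader might also infer more than the documents support:

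- **That there is no exception for any safety reason.** Pregnancy is gated in 5.2.1.4 and 6.7.1, and a liver-specific hold in Appendix C cannot be ruled out.
- **That patients withdrawn from the study must be re-dosed.** Section 3.10 only encourages their procedures. The point concerns IP stops under 3.9.
- **That the hypoglycemia risk follows from the fast alone.** Background metformin/sulfonylurea is held. Section 1.2 associates sulfonylureas with hypoglycemia and describes the study drugs as having a low propensity for it.

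**Conclusion.** The gap is real and worth closing. As written, the plan gives one more full dose of IP to patients who stop it for an AE/SAE, renal or hypoglycemia reason, and nothing supplied withholds it.

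The size per patient is one supervised, closely sampled dose of a drug already being taken. The number of patients is unknown: the plan gives no rate of safety stops. The two active arms hold (21 + 21) / 53 = 79% of planned patients, and a reader might take that as the share at risk. It is only the allocation to active drug.

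The conclusion rests on taking footnote i and section 5.1.8 to govern the early-termination test, as the shared Table 1 row implies. It does not depend on which timing reading of section 3.9.2 is right. It makes no claim about liver stops, and the primary analysis is not affected.

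**What to change.** Add to section 3.9.2 and to Table 1 footnotes a, i and j:

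> When IP is stopped for a safety reason (AE/SAE including ketoacidosis, renal, hypoglycemia, or liver criteria unless Appendix C already provides for it), no IP is given at the early-termination glucose turnover study; the test is limited to the pre-IP period (-180 to 0 min) or omitted if clinically indicated.

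Stops for patient decision or noncompliance can keep the full test. Rescued patients stay on study drug and are not affected.

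The rule turns on the reason for stopping and not on the arm, so no unblinding is needed. For each safety stop it gives up 20 of the 26 glucose/tracer samples, or all 26 if the test is omitted. The primary analysis does not use these values, and pre-IP EGP can still be calculated when the pre-IP period is run.
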